## Method

The study has been approved by the Regional Committees for Medical and Health Research Ethics (REK) ref 2016 / 355.

### Power

Several power analyses have been performed to calculate the required sample size, given an  $\alpha$ -level of 0.05 and power ( $1-\beta$ ) of 0.80. The analyses show that a sample of  $n=150$  will be sufficient to detect standardized regression effects of 0.20 or larger. For intervention effects there will be power to detect effect sizes of  $d=0.40$  or larger. With use of linear mixed effect models and structural equation modelling, and the wait-list design, power will be even higher. Thus, we are confident that the planned sample size is sufficient to address the research questions posed.

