## Aims

The overall aim is to evaluate the effectiveness on mental health of TRT among unaccompanied minor asylum-seekers and refugees.

More specifically, we will:

Examine the short and long-term effectiveness of TRT in reducing mental health symptoms and promote QoL

- *Primary hypothesis:* The TRT intervention is expected to significantly improve the mental health status (i.e. alleviate symptoms of post-traumatic stress disorder, depression and anxiety and promote QoL) compared to the waiting-list control group.
- *Secondary hypotheses:* 1) Asylum- related and post-resettlement psychosocial stressors predict mental health problems and QoL over and above pre-migration traumatic exposure. 2) Asylum-related and post-resettlement psychosocial stressors predict variation in the short and long term effects of the effect of the TRT.

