### Sample

The study involves about 170 UMA and URM  $> 8$  years.

Recruitment involved inviting reception centers and municipalities from all over Norway to participate as a first step. The children in the centers and municipalities that accepted to participate who spoke Pashto, Dari, Arabic, Somali or Tigrinya, were then invited to

participate (see information below).

A total of 18 TRT-groups have been conducted during the project period. To avoid cross-contamination [37] of the intervention, the children were allocated to Intervention or Control groups on an institutional level. We endorsed half of the participating reception centers and resettlement municipalities to Intervention Groups, and the other half to wait-list Control Groups. We did this based on practical considerations related to the data collection, such as time frames of the commission, geographical location of the targeted centers and municipalities, and availability of bilingual research assistants. The Intervention Groups started the TRT soon after the information meeting, and the Control Groups started when they had completed the five weekly sessions and the W2 data collection.

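### The 80% power claimed for a standardized regression effect of 0.20 at n=150 is about 70% for an unadjusted two-sided 5% test, and the plan states neither the sidedness nor the covariate assumptions behind it

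*Combined protocol and SAP*

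**What the plan says.** The Power section opens with "Several power analyses have been performed to calculate the required sample size", at alpha 0.05 and power 0.80. It concludes that n=150 "will be sufficient to detect standardized regression effects of 0.20 or larger". The next sentence makes a companion claim: "For intervention effects there will be power to detect effect sizes of" d=0.40 or more. The section then says, without figures, that mixed models, structural equation modelling and the wait-list design raise power further, and that the sample is adequate for the research questions. It gives no sidedness, number of predictors, covariate R², dropout or intraclass correlation.

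The regression figure bears most directly on the first secondary hypothesis in Aims, that asylum-related and post-resettlement stressors "predict mental health problems and QoL over and above pre-migration traumatic exposure". The Sample section says "The study involves about 170 UMA and URM", allocated by institution, with 18 TRT groups run.

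**The concern.** An alpha of 0.05 with no qualifier is normally read as two-sided. On that reading, with one predictor and no covariate contribution, the stated inputs do not give 80% power. The plan uses this figure to support the adequacy of its sample, and the Progress Plan foresees five articles. If readers take 0.20 as the effect the study could reliably detect, a null result for a stressor may be given more weight than it can bear. In the simple two-sided case a true effect of 0.20 would be missed about 3 times in 10, not 2 in 10.

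**Working it through.** **Inputs from the documents.** Alpha 0.05, power 0.80, n=150, standardized effect 0.20, d=0.40 (Power); about 170 children, half of the institutions to each arm, 18 TRT groups (Sample). Assumed for the base case: one predictor, no variance explained by other predictors, independent children. A single standardized slope of 0.20 is then a correlation of 0.20.

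**Formulas.**
- Fisher z: power = Φ(atanh(r)·√(n−3) − z), with z = 1.645 one-sided and 1.960 two-sided.
- Noncentral t: f² = r²/(1−r²) = 0.04/0.96, noncentrality √(f²·n).

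**Reproducing the plan's figure.** At n=150, atanh(0.20)·√147 = 0.2027 × 12.124 = 2.458, and the noncentrality is √(0.041667 × 150) = 2.50.

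| Test | n | Fisher z | Noncentral t |
|---|---|---|---|
| One-sided | 150 | Φ(2.458 − 1.645) = 0.792 | 0.801 |
| Two-sided | 150 | Φ(2.458 − 1.960) = 0.691 | 0.700 |
| Two-sided | 170 | Φ(2.620 − 1.960) = 0.745 | 0.754 |

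The stated 80% reproduces one-sided. Two-sided, 80% needs 191 (noncentral t) to 194 (Fisher z) children. The effect detectable with 80% power is 0.224–0.227 at n=150 and 0.211–0.213 at n=170.

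**Cross-check on the companion claim.** A correlation of 0.20 corresponds to d = 2(0.20)/√0.96 = 0.41, so the two claims are nearly the same calculation. With 75 per arm (equal arms assumed), unadjusted power for d=0.40 is 0.79 one-sided and 0.68–0.69 two-sided, the same pattern.

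**Effect of other predictors (assumed values; the documents give none).** Let other predictors explain R² of the outcome and correlate ρ with the stressor. The stressor's unique share is 0.04(1−ρ²), and f² = 0.04(1−ρ²) / [1 − R² − 0.04(1−ρ²)]. Two-sided power by noncentral t:

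| R² | ρ | n=150 | n=170 |
|---|---|---|---|
| 0.10 | 0 | 0.75 | 0.80 |
| 0.20 | 0 | 0.80 | 0.84 |
| 0.10 | 0.3 | 0.70 | 0.76 |
| 0.20 | 0.3 | 0.76 | 0.81 |
| 0.30 | 0.3 | 0.81 | 0.86 |
| 0.10 | 0.5 | 0.62 | 0.67 |
| 0.20 | 0.5 | 0.67 | 0.73 |

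**Effect of clustering (assumed ICC).** With 150/18 = 8.3 children per TRT group, the simple design effect is 1 + 7.33 × ICC.
- ICC 0.01: design effect 1.073, effective n 139.8, power 0.66–0.67 two-sided and 0.77–0.78 one-sided.
- ICC 0.05: design effect 1.367, effective n 109.8, power 0.55–0.56 two-sided and 0.67–0.68 one-sided.

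This design effect applies in full only to a predictor shared by the whole group, so it is the harsh end for stressors that differ between children in a group.

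**The case against.** The strongest reply is that nothing has been shown to be miscalculated. The plan never says the test is two-sided, and its figure reproduces almost exactly one-sided. A directional reading is possible: the primary hypothesis is worded as improvement, and the background expects stressors to worsen symptoms and quality of life. Several analyses were run and their covariate assumptions are not reported. A two-sided test with about 20% of variance explained by uncorrelated predictors also gives 0.80. Higher R² offsets moderate correlation, and at n=170 less R² is needed.

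Repeated measurement could help too. There are three waves and mixed models are planned. As an illustration, if the slope is constant and outcomes are averaged over three waves that correlate 0.5–0.7, two-sided power at n=150 is 0.87–0.80.

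These points stand. A reader might infer that the 80% is an arithmetic error, that it can be reached only one-sided, or that the first secondary hypothesis is under-powered outright. The documents support none of these, because the inputs that would settle them are not given.

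The reply does not remove the gap. No section declares a one-sided test, and the first secondary hypothesis states no direction. The claimed gains have no figures, and a wait-list contrast does not by itself sharpen a stressor–outcome slope. Because that hypothesis concerns prediction beyond trauma exposure, collinearity counts against power, and clustering does so even one-sided.

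**Conclusion.** The point holds as an unstated-assumption problem with a measurable consequence. Under the usual reading (two-sided 5%, one predictor, no variance explained by others, independent children), power for 0.20 is 69–70% at n=150 and about 75% at n=170, against the stated 80%. The detectable effect is about 0.22–0.23 and 0.21 respectively. The stated figure needs a one-sided test, or a covariate contribution of roughly 20% of variance if uncorrelated with the stressor and more if correlated. The plan states neither. Whether actual power is above or below 80% cannot be settled from the documents, since collinearity and clustering push it down while covariates and repeated measures may push it up.

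The d=0.40 claim shows the same shortfall only in the unadjusted case; the ANCOVA planned under Statistical Analyses may recover it. The shift in detectable effect is modest and the hypothesis is secondary, but the plan relies on the figure and it is easily corrected.

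**What to change.** Replace the regression sentence in the Power section with:

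> With two-sided alpha 0.05, one predictor, no variance explained by other predictors and independent children, power is 80% for a standardized effect of about 0.22–0.23 at n=150 (0.21 at n=170) and about 70% (75%) for 0.20; clustering within institutions would lower these figures.

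If a one-sided test or a covariate R² was assumed, declare it, with its value, instead. State the sidedness for the d=0.40 claim in the same place. In the articles, interpret null stressor results by confidence intervals and not against 0.20.

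The cost is one or two sentences and a slightly less favourable stated figure. The Progress Plan lists data collection as completed, so the remedy concerns reporting and interpretation; no new data are needed.

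### The 80% power for d=0.40 at n=150 matches a calculation for independent children and makes no allowance for allocation by institution

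*Combined protocol and SAP*

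**What the plan says.** The Power section gives alpha 0.05, power 0.80 and n=150, and then: "For intervention effects there will be power to detect effect sizes of $d=0.40$ or larger". It adds "With use of linear mixed effect models and structural equation modelling, and the wait-list design, power will be even higher" and concludes "we are confident that the planned sample size is sufficient to address the research questions posed". It does not state sidedness, a correlation between W1 and the outcome, an ICC, a design effect or a number of institutions.

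The Sample section says that "the children were allocated to Intervention or Control groups on an institutional level", and "We endorsed half of the participating reception centers and resettlement municipalities to Intervention Groups, and the other half to wait-list Control Groups". It reports "A total of 18 TRT-groups have been conducted during the project period" and "The study involves about 170 UMA and URM", but not how many institutions took part. On the control arm it says "the Control Groups started when they had completed the five weekly sessions and the W2 data collection".

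Procedures places a questionnaire before treatment (W1). Statistical Analyses names ANCOVA and mixed regression, and ties dependency to the repeated measurements only; institution and TRT group are not mentioned. The Progress Plan lists data collection as completed.

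**The concern.** Children in the same center or municipality share staff, surroundings and a TRT group, so their outcomes may be correlated. When whole institutions are allocated, that correlation enters the variance of the between-arm comparison, and the number of institutions limits the degrees of freedom. A power figure for independent children is then too high unless something else makes up the loss.

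The plan moves the other way and claims additional power from modelling and from the wait-list design. A mixed model that accounts for variance between institutions does not by itself lift power above an independent-children figure. Controls are treated only after W2, so their treatment adds nothing to the between-arm contrast at W2, and no other estimate that uses later control data is named.

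With the data already collected, the stake is interpretation. A reader who takes 80% at face value would treat a non-significant result as stronger evidence against d=0.40 than the design may support.

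**Working it through.** **Inputs from the plan:** alpha 0.05, d=0.40 (so SD=1), n=150 (Power); about 170 children, 18 TRT groups, half of the institutions per arm (Sample).

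**Assumed, because the plan gives no value:** equal numbers of children per arm; no dropout; ICC 0.02 and 0.05; r = 0 or 0.5, the same at child and institution level; K=18 equal clusters. Eighteen is the number of TRT groups, which need not equal the number of institutions.

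**Step 1. The plan's figure, independent children.** The variance of the difference is 4(1−r²)/n. Power comes from the noncentral t with n−2=148 df and noncentrality 0.40/√variance.
- r=0: variance 4/150=0.0267, noncentrality 2.45. Power is 68% two-sided and 79% one-sided.
- r=0.5: variance 0.0267×0.75=0.0200, noncentrality 2.83. Power is 80% two-sided.

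The stated figure is therefore reproduced one-sided, or two-sided with r of at least about 0.5. The companion claim, a standardized regression effect of 0.20 at n=150, gives 79% one-sided and 69% two-sided when treated as a correlation (Fisher z), so it also fits a one-sided calculation.

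**Step 2. Add allocation by institution.** The variance is (4/K)×[ICC(1−r²) + (1−ICC)(1−r²)/(n/K)], with K−2=16 df and n/K=150/18=8.33.
- ICC 0.02, r=0: (4/18)×[0.02 + 0.98/8.33] = 0.0306, noncentrality 2.29.
- ICC 0.05, r=0: (4/18)×[0.05 + 0.95/8.33] = 0.0364, noncentrality 2.10.
- For r=0.5, multiply each variance by 0.75.

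Power at n=150:

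| | Independent | ICC 0.02 | ICC 0.05 |
|---|---|---|---|
| Two-sided, r=0 | 68% | 58% | 50% |
| Two-sided, r=0.5 | 80% | 70% | 62% |
| One-sided, r=0 | 79% | 71% | 64% |
| One-sided, r=0.5 | 88% | 81% | 75% |

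Two-sided, clustering costs about 10 to 11 points at ICC 0.02 and about 18 at ICC 0.05. About half of the loss at ICC 0.02 comes from having 16 df: with ICC 0 and 16 df, two-sided power is already 63% (r=0) or 76% (r=0.5).

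**Step 3. Sensitivity.**
- At n=170, two-sided power is 62% or 74% (r=0 or 0.5) at ICC 0.02, and 54% or 66% at ICC 0.05.
- With 12 to 30 clusters at n=150, two-sided power is 51–62% (r=0) or 63–75% (r=0.5) at ICC 0.02, and 42–58% or 53–70% at ICC 0.05.
- With child-level r=0.5 and institution-level r=0.8 at n=150, two-sided power is 73% at ICC 0.02 and 70% at ICC 0.05.
- The r that restores 80% two-sided is about 0.64 (n=150) or 0.59 (n=170) at ICC 0.02, and 0.71 or 0.68 at ICC 0.05.

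**Step 4. Detectable d at 80% power, two-sided, 18 clusters, n=150, for r=0.5 to 0.** It is 0.45–0.52 at ICC 0.02 and 0.49–0.57 at ICC 0.05. For independent children it is 0.40–0.46.

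**The case against.** The strongest reply is that the plan's figure can be reproduced, so this is not a slip in arithmetic, and that the planned baseline adjustment may recover the loss. Both Power figures fit a one-sided calculation without adjustment. If that is what was done, ANCOVA on W1 is a real gain on top: one-sided with r=0.5, clustered power is 81% at ICC 0.02 and 75% at ICC 0.05.

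This stands, and it rules out two stronger readings. A reader might infer that 80% can hold only if children are independent. It cannot be put that way, because a high enough W1 correlation, or one-sided testing with adjustment, reaches 80% under some clustered scenarios. A reader might also infer that the study is shown to be underpowered. The documents give no ICC, r or institution count, so they cannot show that. The percentages are scenarios, not bounds, and unequal group sizes are not modelled.

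Two further points are fair. The wait-list gain is unexplained rather than shown to be wrong, and nothing here shows that structural equation modelling could not help. Also, no sample-size decision remains, and the plan does not say that it will judge null results by the 80% figure.

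What the reply does not supply is the missing assumptions. The plan states neither a one-sided test nor a value of r. If r=0.5 is already inside the 80%, it cannot be counted again as an extra gain.

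**Conclusion.** The concern holds as a failure to allow for clustering and to state the conditions behind the figure. The 80% matches an independent-children calculation, and clustering lowers it under either reading that reproduces it: at ICC 0.02, from 79% to 71% (one-sided, unadjusted) or from 80% to 70% (two-sided, r=0.5). At ICC 0.05 the corresponding values are 64% and 62%.

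These sizes rest on 18 equal clusters, 16 df, n=150 and assumed ICCs. The omission itself is certain; the size of the shortfall is not, and a higher W1 correlation could remove it. The claim of still higher power is not supported for the wait-list design, nor for a mixed model merely because it accounts for institutions. It is worth correcting before results are interpreted.

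**What to change.** 1. **Power, intervention sentence.** Restate it with sidedness, the actual number of institutions per arm, an ICC range and the assumed W1 correlation, and give the resulting detectable d. The form could be: two-sided 0.05, n=150, 18 clusters, 80% power, detectable d 0.45–0.52 at ICC 0.02 and 0.49–0.57 at ICC 0.05 for r=0.5 to 0. Recompute these values with the real institution count.
2. **Power, claim of higher power.** Keep it only for gains not already counted in the 80%. State which estimate gains from the wait-list design, or remove that phrase.
3. **Power, conclusion.** Qualify the confidence in the sample size for the intervention effect.
4. **Statistical Analyses.** Include institution as a random effect, or use cluster-robust inference with a small-sample correction. Judge a non-significant result by that confidence interval, not by the 80% figure.

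The cost is some text, one recalculation with an institution count that the sponsor can establish, and one added model term. No new children or data are needed. The downside is that the stated figure becomes less favourable and intervals may be wider.

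### The Power section calls the sample sufficient for every research question, but gives no effect size or power for secondary hypothesis 2, a treatment-by-stressor interaction that reaches 80% power only if it is about as large as the whole planned TRT effect

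*Combined protocol and SAP*

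**What the plan says.** The Power section takes a 5% significance level and 80% power. It gives two results for n = 150. The sample "will be sufficient to detect standardized regression effects of 0.20 or larger", and for intervention effects it can detect d = 0.40 or larger. It adds, without a figure, that mixed models, structural equation models and the wait-list design will raise power further. It then concludes: "Thus, we are confident that the planned sample size is sufficient to address the research questions posed".

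One of those questions is secondary hypothesis 2 in the Aims: "Asylum-related and post-resettlement psychosocial stressors predict variation in the short and long term effects" of TRT. The plan gives no interaction size, no power calculation named for an interaction, no sidedness, no baseline-outcome correlation and no intracluster correlation (ICC). Statistical Analyses names ANCOVA and mixed regression but no interaction term.

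The Sample section describes allocation by institution: "We endorsed half of the participating reception centers and resettlement municipalities to Intervention Groups, and the other half to wait-list Control Groups". It puts the number of children at about 170 and the number of TRT groups at 18.

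**The concern.** Variation in a treatment effect according to stressor level is a difference between two arm-specific slopes. Its standard error is twice that of a single slope estimated in the whole sample. A calculation for one regression slope, or for the average intervention effect, therefore does not carry over to it without a further step, and the plan does not show that step.

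The question matters to this study. The background says that stressors may interfere with the effectiveness of TRT. The section on TRT reports a small earlier study that suggested less benefit in asylum-seekers than in refugees, and lists the psychosocial context among the extensions of this design. If the interaction is not significant and the plan has declared the sample sufficient, the result can be mistaken for evidence that TRT helps equally at all stress levels.

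**Working it through.** **Inputs from the plan (Power).** n = 150; alpha 0.05; power 0.80; intervention effect d = 0.40; standardised regression effect 0.20. Sidedness is not stated.

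**Assumptions.** 75 children per arm (the plan allocates half of the institutions to each arm, not half of the children); stressor scaled to SD 1 in each arm; residual SD 1; no clustering; normal approximation. Baseline adjustment, where used, has correlation r = 0.5, which gives residual SD √(1 − 0.25) = 0.866.

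**Step 1: the plan's own figures.**

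| Test at n = 150 | Power for d = 0.40 | Total n for 80% |
|---|---|---|
| Two-sided, unadjusted | 68.8% | 198 |
| One-sided, unadjusted | 78.9% | 156 |
| Two-sided, r = 0.5 | 80.7% | 148 |

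For a standardised slope of 0.20 (noncentral t, noncentrality 0.20/√0.96 × √150 = 2.50), power is 70.0% two-sided and 80.1% one-sided. The stated 80% is therefore reproduced, to within about a point, but only under a one-sided test or with baseline adjustment. The plan states neither.

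**Step 2: standard error of the interaction.**
- One arm's slope: 1/√75 = 0.115.
- Difference of two slopes: √(1/75 + 1/75) = 2/√150 = 0.163.
- One slope in all 150 children: 1/√150 = 0.082, half of that.

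**Step 3: change in TRT effect per SD of stressor detectable with 80% power.**
- Two-sided: (1.960 + 0.842) × 0.163 = 0.457.
- Two-sided, r = 0.5: 0.457 × 0.866 = 0.396.
- One-sided: (1.645 + 0.842) × 0.163 = 0.406.

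With an average effect of 0.40, a change of 0.457 per SD means an effect of 0.40 − 0.457 = −0.06 at one end of ±1 SD of stressor and 0.40 + 0.457 = 0.86 at the other.

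**Step 4: power over a range of assumed interactions.** Two-sided power is Φ(δ/SE − 1.96) + Φ(−δ/SE − 1.96), with SE = 0.163, or 0.163 × 0.866 = 0.141 when r = 0.5.

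| Change per SD (δ) | TRT effect at −1 SD / +1 SD if the average is 0.40 and stress weakens it | Two-sided | Two-sided, r = 0.5 |
|---|---|---|---|
| 0.10 | 0.50 / 0.30 | 9% | 11% |
| 0.20 | 0.60 / 0.20 | 23% | 29% |
| 0.30 | 0.70 / 0.10 | 45% | 56% |
| 0.40 | 0.80 / 0.00 | 69% | 81% |

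One-sided and unadjusted, δ = 0.20 gives Φ(0.20/0.163 − 1.645) = 34%.

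**Step 5: sensitivity at δ = 0.20, two-sided.**
- N = 170: SE = 2/√170 = 0.153; power 26% (33% with r = 0.5).
- Clustering: if a full design effect applied, with 18 groups of 150/18 = 8.3 children, an ICC of 0.01, 0.05 or 0.10 (assumed) would give 22%, 18% or 15%. A stressor that varies within groups may incur less than the full design effect.
- Stressor scale relevant to only 75 children (assumed): SE = 2/√75 = 0.231; power 14%. Under Predictors, the asylum-related and post-resettlement stressors are separate instruments, so this could arise.

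**The case against.** The strongest reply is that the regression figure of 0.20 is worded generally and listed apart from intervention effects, so it may be meant to cover a product term. A reader might infer that the plan's figures are main effects only, but the text does not say so. On the generous reading, with equal arms the treatment indicator has SD 0.5. A standardised product coefficient of 0.20 then corresponds to 0.20/0.5 = 0.40 SD per SD of stressor, with power of 69% (81% with r = 0.5). This stands as a possible reading. It still makes the sample sufficient only for moderation as large as the whole planned effect, and only under assumptions that are not stated.

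A second reply is that controls also receive TRT after W2, so hypothesis 2 could be tested as prediction of response among treated children, using a single slope. That would not test variation in the effect of TRT. A stressor that predicts the course of symptoms with or without treatment would give the same slope.

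A third reply is that the plan gives no interaction size, so no single power figure can be held against it. This is correct. A reader might infer that n = 150 has 23% power for hypothesis 2, but that figure belongs to one assumed slope difference, 0.20, tested two-sided without adjustment. Nor are the calculations uniformly favourable or unfavourable to the plan. They leave out clustering, which could lower power, and the main rows leave out baseline adjustment and the larger sample, which would raise it.

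**Conclusion.** The concern holds as a claim that the plan does not support for one named hypothesis. Under the assumptions listed, n = 150 has 80% power only if the TRT effect changes by about 0.46 SD per SD of stressor, or about 0.40 with r = 0.5 or a one-sided test. That is as large as the planned d = 0.40. For smaller interactions, from 0.10 to 0.30 per SD, two-sided power runs from 9% to 45% unadjusted and from 11% to 56% with r = 0.5. About 170 children would change this little.

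The documents do not support saying that the interaction is of any particular size, or that hypothesis 2 cannot be studied. They also do not show that the stated main-effect figures are wrong, only that those figures need assumptions the plan leaves out.

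**What to change.** In Power, take hypothesis 2 out of the closing sentence. State the interaction detectable with 80% power at the actual n, together with sidedness, baseline correlation and ICC.

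State the same assumptions for d = 0.40. Merely narrowing the sentence to main effects would leave in place a figure that has about 69% power under a two-sided unadjusted test.

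In Statistical Analyses, name the treatment-by-stressor term and report its W2 estimate with a 95% CI. W2 is the appropriate wave because controls start TRT after it, so W3 may have no untreated comparison. State that a non-significant interaction will not be read as equal benefit across stress levels. At n = 150, unadjusted, the CI would extend about 1.96 × 0.163 = 0.32 SD per SD on either side of the estimate, which shows the reader what a null result leaves open.

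The cost is a few sentences and a less favourable stated figure. The Progress Plan records data collection as complete, so n is fixed, and no new data are needed.
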